II. Research Plan and Design

A. Study Objectives: List the broad research goal and specific aims of the project in a clear, concise manner using lay language. List primary and secondary; include statement of purpose. (NOTE: the Department of Biostatistics is available to assist with study design, sample size calculation, and statistical analysis matters. Contact [name] or see Consulting and Collaboration at Department of Biostatistics

Primary objectives: To determine if administration of Rifaximin for the period of 10 days reduces serum TMAO levels.

Secondary Objectives: To determine if Rifaximin additionally alters urine TMAO, serum endotoxin,IL-6, IL-8, TNF-alpha, and the composition of the intestinal flora and the composition of the intestinal flora as compared to placebo.

B. Study Type and Design: Indicate type of study (e.g. cross-sectional vs. longitudinal; multicenter, controlled, cross-over, randomized, chart review, case cohort, non-interventional, etc) and describe how the study is to be conducted to accomplish specific aims of the project.

This is a prospective, randomized, placebo-controlled, double-blinded interventional pilot study.

C. Sample size, statistical methods, and power calculation

1. Describe the analytic and statistical methods to be used, including the method of randomization and randomization ratio (1:1; 3:1; etc) if randomization is used.

We seek to enroll a total of 30 patients for this investigation, 15 participants will receive Rifaximin and 15 control patients will receive placebo with a 1:1 randomization ratio. No prior data are available on the impact of rifaximin on serum TMAO levels in CKD patients; therefore, our sample size determination is based on a conservative estimate of the predicted change in TMAO and the expected response variability between study participants. Based on an expected true mean change in serum TMAO concentrations in matched pairs of -30% with a standard deviation of -30% change, we will need to study 13 subjects to be able to reject the null hypothesis that this response difference is zero with 90% power and type I error probability of 0.05. We plan to enroll 15 subjects in our intervention groupin case the observed variability in this response is greater than our initial prediction.

2. If blinding (masking) is involved, describe the procedures, indicate who has the code to the blind, and the circumstances and procedures for breaking the code.

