Blinding will be involved in this study. The primary investigator, study participants, and team members involved in serum/urine end point analyses will be blinded to treatment arm. The investigational pharmacy is responsible for study group assignment and is not blinded. The study team member involved in the fecal bacterial genome analysis will not be blinded, as knowledge of treatment arm will be necessary for the accurate assessment of changes in fecal microbiome composition among study participants.

3. State the maximum number of subjects to be enrolled in each group. Include power calculations to explain what can be studied with the proposed sample size and specify the statistical tests that will be used to test **each** hypothesis. If the research project needs to be pilot tested, state how many subjects will be enrolled in the pilot test and how the procedures for the pilot test will differ from those used in the research protocol.

There will be a total of 30 subjects enrolled; 15 participants will receive Rifaxmin and 15 will receive placebo.

D. Subject Criteria (See Vulnerable Populations appendix, if applicable): Include age range, gender, disease, and stage of treatment. Justify excluding subjects based on race or

gender (including child-bearing potential for women), age (children), or non-English speakers.

- 1. Inclusion criteria: State the criteria for inclusion in the study in a specific and detailed manner.
 - Patients 18 years of age or older
 - Stage IV-V chronic kidney disease (eGFR ≤ 39 ml/min/1.73m²)
- 2. Exclusion criteria: State the criteria for excluding potential subjects from the study in a specific and detailed manner.
 - Patients with normal renal function or those with less advanced kidney disease
 - Inability or unwillingness to provide consent
 - Patients undergoing hemodialysis or peritoneal dialysis therapy or those who have undergone organ transplant
 - Patients who may be pregnant
 - Hemodynamically unstable patients
 - Patients with liver failure, pancreatic insufficiency, or inflammatory bowel disease
 - Patients with ongoing or recent infection and those with history of C-diff infection
 - Patients with abnormal bowel structure secondary to surgical or anatomic variations
 - Patients on certain medications including immunosuppressants, antidiarrheal agents, and current or recent (within the last 2 months) use of antibiotics

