D. Procedures to protect subject confidentiality: Identify any part of the study that may place subject confidentiality at risk. Describe study procedures to protect subject confidentiality.

The researchers will only use and share information that is needed for the study. Identifying information collected may include such information as name, address, phone, date of birth, or other identifiers. Participants health information will be reviewed at KUMC by [name], members of the research team, The University of Kansas Hospital Medical Record Department, the KUMC Research Institute and officials at KUMC who oversee research, including members of the KUMC Human Subjects Committee and other committees and offices that review and monitor research studies. Data will be de-identified prior to analysis and prior to outside involvement in the study.

E. Quality Assurance / Monitoring

1. Describe steps to be taken to assure that the data collected are accurate, consistent, complete and reliable. (source data verification, audits or self – assessment)

Self-assessment.

2. Describe whether there are plans to have ongoing third party monitoring.

There is no plan for third party monitoring.

V. Data Analysis and Reporting

A. Statistical and Data Analysis: A description of the statistical methods to be employed in data analysis, including timing of any planned interim analysis

The study will be considered complete when the necessary power is obtained. A paired, two-sided Student's t-test will be used to compare differences in pre-antibiotic and post-antibiotic TMAO levels.

B. Outcome: Describe what results are expected, the criteria for success or failure and the end point of the study.

We expect that our intervention will lead to significant short-term reductions in serum TMAO levels.

C. Study results to participants: List any study results to be given to subjects and indicate how, when and why they will be given.

Study findings may be discussed at the conclusion of the study by participant request.

D. Publication Plan: Describe plans for publication of research results.

Results may be published in abstract form or as part of a peer-reviewed original research manuscript.

- **VI. Bibliography / References / Literature Cited** (choose the applicable title and list citations according to APA or other accepted style in your discipline)

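### The 90% power figure belongs to a one-arm before/after test; power for the randomised 15 vs 15 comparison is never stated, and is about 75% if placebo has mean change 0 and the same SD of 30%

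*Combined protocol and SAP*

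**What the plan says.** Section II.B sets the design: "This is a prospective, randomized, placebo-controlled, double-blinded interventional pilot study". Section II.C.3 fixes its size: "There will be a total of 30 subjects enrolled; 15 participants will receive Rifaxmin and 15 will receive placebo".

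The only power calculation is in II.C.1. It takes an expected mean change in serum TMAO of -30% in matched pairs, "with a standard deviation of -30% change" (the minus sign must be a slip, since an SD cannot be negative), and a type I error of 0.05. It concludes that "we will need to study 13 subjects to be able to reject the null hypothesis that this response difference is zero with 90% power". The step from 13 to 15 is explained for one arm only: "We plan to enroll 15 subjects in our intervention groupin case the observed variability in this response is greater than our initial prediction".

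Section V.A names a single test: "A paired, two-sided Student's t-test will be used to compare differences in pre-antibiotic and post-antibiotic TMAO levels". It also gives the completion rule: "The study will be considered complete when the necessary power is obtained".

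The template text at II.C.3 asks for power calculations and for the test of each hypothesis; the answer gives arm sizes only. Comparison with placebo is mentioned in the secondary objectives (II.A), but no test is attached to it.

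**The concern.** The power calculation and the named test agree with each other, but neither uses the placebo arm. The primary objective in II.A is causal: does ten days of rifaximin reduce serum TMAO? In a randomised trial the placebo group is there to answer that, because TMAO may change between Day 0 and Day 11 for reasons unrelated to the drug. A before/after test in the treated arm counts any such change as drug effect.

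Two things are at stake. First, 90% is the only power figure offered for a placebo-controlled trial, so it is easily read as the chance of detecting a rifaximin-placebo difference, which it is not. Second, nothing in the plan supports the choice of 15 placebo patients, so nobody can judge what the randomised comparison can show.

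The completion rule is a separate but neighbouring problem. Power is a property of the design and the assumptions, not something that is observed to arrive. Read literally, the sentence could allow enrolment to stop or continue according to the data.

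**Working it through.** **Inputs from the protocol.** Rifaximin mean change -30%, SD 30%, alpha 0.05 (II.C.1); two-sided paired t-test (V.A); 15 per arm, 1:1 (II.C.1 and II.C.3). **Not in the protocol, so assumed:** placebo mean change and placebo SD. All power values below use the noncentral t distribution, two-sided 0.05.

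**1. The protocol's own figure.** For a paired test the noncentrality is λ = (|mean change|/SD)·√n, with n - 1 df.
- n = 12: λ = (30/30)·√12 = 3.464; power 88.3%.
- n = 13: λ = √13 = 3.606, 12 df, critical t 2.179; power 91.1%.
- n = 15: λ = √15 = 3.873; power 94.9%.

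So 13 is the smallest n that reaches 90%, and the stated figure is reproduced.

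**2. The randomised comparison.** For a difference D between arms, SE = √(SD_R²/15 + SD_P²/15) and λ = D/SE. With SD 30 in both arms and placebo mean 0, SE = √(900/15 + 900/15) = √120 = 10.95 and λ = 30/10.95 = 2.74. With 28 df and critical t 2.048, power is **75.3%**.

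**3. Other placebo SDs** (rifaximin -30, SD 30; placebo mean 0; Welch test with Satterthwaite df):

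| Placebo SD (%) | SE | λ | Power |
|---|---|---|---|
| 10 | 8.16 | 3.67 | 93% |
| 15 | 8.66 | 3.46 | 91% |
| 20 | 9.31 | 3.22 | 87% |
| 25 | 10.08 | 2.98 | 82% |
| 30 | 10.95 | 2.74 | 75% |
| 40 | 12.91 | 2.32 | 61% |

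Power reaches 90% only if the placebo SD is about 16 or less, roughly half the SD assumed for rifaximin. The difference detectable with 90% power is 29.5, 31.4, 36.8 and 43.5 points at placebo SD 15, 20, 30 and 40.

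**4. Downward change on placebo.** Here -30% is read as the total change on rifaximin, so a fall on placebo shrinks the difference. A placebo change of -5 leaves D = 30 - 5 = 25: power is 79%, 73%, 60% and 46% at placebo SD 15, 20, 30 and 40. A change of -10 leaves D = 20: power is 42% at SD 30.

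**5. What the one-arm test does when the drug has no effect.** Take n = 15, SD 30 and a non-drug fall (assumed) of 5 or 10 points. Then λ = (5/30)·√15 = 0.645 or (10/30)·√15 = 1.291, and the paired test rejects in 9% or 23% of trials instead of 5%.

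**6. Further sensitivity, placebo mean 0.** With 13 evaluable patients per arm and SD 30 in both, power is 69%. With 15 per arm and SD 40 in both, it is 51%. With SD 30 in both arms, 80% power needs 17 per arm and 90% needs 23 (22 falls just short, at 89.97%).

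**The case against.** The best defence is that nothing is mislabelled. The primary aim is the post-minus-pre change after rifaximin, the calculation refers to matched pairs, V.A names a paired test, and the 15 are tied to the intervention group. On that reading 90% is the power of the planned analysis, and a pilot need not be powered for more. The consistency is real. But it means the primary question is answered without the randomised control. A pilot may have modest power for its randomised comparison, but it should say what that power is.

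Second, 75% is one assumed point. II.C.1 describes variability in the response to rifaximin, which placebo patients need not share; with a placebo SD of 15 to 20 the power is 91% to 87%, close to the stated figure. This stands as a caution: the documented gap is that between-arm power is not stated, and 75% is the reference case if the protocol's own SD is used in both arms. The error can also go the other way, since the protocol itself allows for more variability on rifaximin than predicted.

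Third, the figures for a fall on placebo depend on reading -30% as the total change on rifaximin. If -30 is the drug effect alone and both arms drift equally, the difference stays at 30 and power is unchanged. That qualification is right.

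Fourth, the completion sentence may only mean reaching the planned number. Possibly so, in which case it should state the number.

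**Conclusion.** The concern holds and should be fixed before analysis. The sample-size arithmetic is correct for a one-arm paired test, but that power does not carry over to the randomised comparison, for which the protocol states neither a test nor a power. That gap needs no assumption to establish.

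Its size does depend on assumptions. If placebo has mean change 0 and SD 30%, and all 30 patients are evaluable, the chance of missing a true 30-point difference between arms is about 25% (100 - 75.3), not 10%. Over placebo SDs of 15 to 40 with the rifaximin SD held at 30, power runs from 91% to 61%; withdrawals or a larger rifaximin SD would lower it further. The trial can run at its present size, provided its primary result rests on the placebo comparison and its power is described as such.

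**What to change.** Keep 30 patients.

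**In V.A, replace both sentences with:**

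> Primary analysis: the difference between arms (rifaximin minus placebo) in change in serum TMAO from Day 0 to Day 11, as percent of Day 0, by a two-sided two-sample (Welch) t-test at 0.05. Within-arm paired t-tests are descriptive. The study is complete when 30 randomised participants have completed Day 25 or withdrawn. There will be one final analysis and no interim analysis of TMAO.

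**In II.C.1, state:**

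> With 15 evaluable participants per arm this test has about 75% power for a between-arm difference of 30 percentage points, assuming SD 30 in both arms; 90% power applies to a difference of about 37 points. No placebo data are available: a placebo SD of 15, 20 or 40 gives about 91%, 87% or 61%. With 13 evaluable per arm and SD 30 in both, power is about 69%. The figure of 13 subjects at 90% applies only to the descriptive within-arm paired test.

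Percent change is proposed because the power inputs are in percent; the primary aim, now worded as a difference in concentrations, should name the same scale. A baseline-adjusted comparison of the arms would also be valid if specified in advance.

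The cost is text only: no added patients, visits or samples. The price is a stated power of about 75% instead of 90%, and a paired test that becomes descriptive. If the sponsor wants a higher between-arm power under the equal-SD assumption, the sizes in step 6 of the working apply: 17 per arm for 80% (34 in total) or 23 per arm for 90% (46 in total), before any allowance for withdrawals.

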University of Kansas Medical Center RESEARCH PROTOCOL INVOLVING HUMAN SUBJECTS TEMPLATE WITH GUIDANCE

Version date: 8/11/2015

Principal Investigator: [name].

Study Title: Impact of Rifaximin Therapy on Intestinal Byproducts in Chronic Kidney Disease

Co- Investigator(s): [name], D.O.

[name], M.B., BChir [name]. [name] [name] [name]

(NOTE: not all sections of this template will apply to all projects. "N/A" is an acceptable response.)

I. Purpose, Background and Rationale

A. Aim and Hypotheses

1. Begin with a brief introduction to describe the origin and importance of the study.

Trimethylamine-N-oxide (TMAO) is a circulating organic compound produced by the metabolism of dietary L-carnitine and choline. TMAO was recently identified to directly induce atherosclerosis in rodents and is strongly associated with the incidence of cardiovascular events in humans. The proposed investigation is a prospective pilot study to assess the impact of alterations in the intestinal flora by short-term antibiotic suppression (with Rifaximin) and to measure its effect on serum TMAO levels in patients with advanced-stage (stage IV-V) chronic kidney disease.

2. Clearly state the aim(s) and hypothesis(es), listing them by number if there is more than one.

Hypothesis: Treatment of CKD patients with Rifaximin will suppress the bacterial flora that are responsible for the generation of trimethylamine, a TMAO precursor, and subsequently reduce serum TMAO concentrations.

Primary Aim:

 The primary outcome of interest will be the change in serum TMAO concentrations (post-therapy minus pre-therapy TMAO) following Rifaximin administration for 10 days.

Secondary Aims:

- 1. To measure the change in urine TMAO
- 2. To measure the change in serum endotoxin, IL-6, IL-8, TNF-alpha levels
- 3. To measure the alteration of bowel microbiota
- 4. To assess the above changes in steady state, 2 weeks after completion of therapy

B. Background and Significance

1. Study Significance: what the proposed research is intended to accomplish and the importance of the results

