- 3. Withdrawal/Termination criteria: Include the specific circumstances in which the subject's participation will be terminated by the investigator. Include any necessary safety precautions to be applied to those who withdraw (tapering drug doses, evaluative x-ray, etc.)
 - Participation may be terminated if subject is found to not meet the inclusion or exclusion criteria. Participants may withdraw at any time.
- 4. Clarify whether a study subject may participate in another research study while participating in this research study.
 - Patients should not participate in another research study while taking the study medication but exceptions may be made dependent on the nature of the other research study.

E. Specific methods and techniques used throughout the study

1. Laboratory tests: Methods for collecting specimens and data. Indicate purpose, amount and timing of tests performed (e.g., blood tests, urine tests, CSF tests, EKGs, etc.). Include specific test components and estimated volume and type of specimens needed for each test.

Serum and urine samples (30ml each) will be collected at the baseline and post-therapy visits (day 0, day 11, and day 25) for measurement of TMAO, endotoxin, IL-6, IL-8, and TNFa levels. Fecal specimens will be collected at these same time points in order to assess changes in the intestinal microbiome after administration of Rifaximin.

2. Study Procedures: Describe each procedure to be used in the study, including the instruments used, time required for each procedure, cognitive assessments, etc.

Blood, urine and stool samples will be collected for analysis. Aside from venipuncture there will be no other procedures.

3. Clearly indicate which procedures, tests, visits, etc., are parts of usual standard therapy and which are performed solely for research purposes. Make it clear which tests are routinely performed for clinical care but are providing data for the research (and are billable to insurance companies), and which tests are only performed for research purposes (not billable to insurance companies).

Any samples collected during the specified research appointments will be used for research purposes only and will not be billed.

4. Describe the fate of any body component (blood, CSF, bone marrow, etc.) used in the study, emphasizing confidentiality of labeling of the sample and the sample's destruction or storage.

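### The microbiome analyst is left unblinded for a reason that does not require it, and the plan does not say when the arm is revealed

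*Combined protocol and SAP*

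**What the plan says.** Section II.C.2 blinds the primary investigator, the participants and the laboratory staff for the other endpoints: "team members involved in serum/urine end point analyses will be blinded to treatment arm". Of the assignment it says: "The investigational pharmacy is responsible for study group assignment and is not blinded". It then makes one exception: "The study team member involved in the fecal bacterial genome analysis will not be blinded, as knowledge of treatment arm will be necessary". The ground offered is accuracy in judging how the stool flora change.

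The endpoint concerned is secondary aim 3 in section I.A, "To measure the alteration of bowel microbiota", together with the microbiota part of aim 4, "To assess the above changes in steady state, 2 weeks after completion of therapy". Section II.A makes it a between-arm question: "the composition of the intestinal flora as compared to placebo". Section II.E.1 places stool sampling on the same days as serum and urine (0, 11 and 25): "Fecal specimens will be collected at these same time points in order to assess changes in the intestinal microbiome after administration of Rifaximin".

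**The concern.** The protocol describes the trial as double-blinded, and its hypothesis is that rifaximin suppresses the flora that generate the TMAO precursor. The stool result is the direct evidence for that step. It is also the one measured endpoint whose analyst is allowed to know the arm.

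Sequencing output may be objective, but several decisions around it are not: which specimens fail quality checks, how reads are filtered, which taxa or diversity measures are reported. Section V.A names a test for TMAO only, so none of these is settled in advance. If they are made by someone who knows the arm, a reported difference from placebo is open to challenge, and the trial could not show that the choices were independent of the result.

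**Working it through.** The plan gives no figure on this point, so the check is mainly a reading of the text. The counts below show reach only.

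**1. Does measuring change need the arm?** Within-participant change is the day 11 or day 25 result set against day 0 for the same person. The inputs are study ID and visit. Section II.E.4 labels stool with study information and the study ID. The arm is not needed.

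**2. Does the comparison with placebo need the arm?** It needs to know which participants belong together. A code of A or B supplies that. Which code is rifaximin need be known only for interpretation.

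**3. Do the other laboratory analysts manage without it?** The serum and urine analysts assess change at the same three visits and are blinded (II.C.2, II.E.1). The parallel is not exact: their measures are single levels, whereas composition is multivariate. But multivariate data leave more choices to the analyst, which is a reason for masking.

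**4. Is a step named that needs the true arm?** No processing, sequencing, bioinformatic or comparison step is named.

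**5. Is the time of unblinding stated?** The prompt in II.C.2 asks for the circumstances and procedures for breaking the code. The answer gives neither. The exception could mean that the arm is known throughout, or only at the final comparison.

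**6. Does another section close the gap?**
- IV.B refers to microbiome analysis at a future time. That fits analysis after collection, but does not say the arm is withheld until then.
- IV.A.1 and IV.D de-identify data before analysis. That hides the person, not the arm.
- V.A gives no microbiome method, so exclusions and the choice of measure remain open.

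**7. Reach.**
- Secondary measures in I.A: urine TMAO (1) + endotoxin, IL-6, IL-8 and TNF-alpha (4) + bowel microbiota (1) = 6. One is assessed unblinded and 5 are assessed blinded. Aim 4 repeats measures at day 25 and can also cover serum TMAO, which is read blinded.
- Stool specimens, at one per participant per visit with 15 per arm (II.C.1): 30 × 3 = 90.
- Day 0: 30 specimens, taken before study drug, where masking can be complete.
- Days 11 and 25: 30 × 2 = 60, or 15 × 2 = 30 per arm, where the drug's effect may reveal the arm.

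**The case against.** There is a fair case for treating this as a minor clarification.

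- **It is disclosed and reasoned.** The exception is stated openly and does not contradict the rest of II.C.2. Its wording can be read to mean only that whoever compares the groups must know the groups. On that reading it is mild. It still calls for a group code and not the true arm, so the reason falls short either way.
- **The two complaints rest on different readings.** If the analyst is never blinded, there is no later reveal whose time could be missing. This is partly right. The missing time is a side point, and the unsupported reason carries the weight.
- **The real gap is the lack of a microbiome analysis plan.** A plan fixed in advance would remove much of the risk even with an unblinded analyst, and blinding alone would leave the choice of measure free. This stands, which is why the fix ties the release of codes to written rules. The two weaknesses make each other worse.
- **Handling specimens with the arm known is inferred.** No section describes processing by arm, and stool labels are not said to carry it. True, but nothing prevents it either.
- **Masking may fail where it matters.** Rifaximin is expected to alter the flora, so the arm may be guessed from the 60 post-treatment specimens. This stands and limits the gain. Rules fixed before codes are released still protect the analysis if the arm is guessed later.
- **The stakes are modest.** It is one secondary laboratory measure in a 30-patient pilot, with no demonstrated bias. This stands and sets the level of the recommendation.

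**Conclusion.** The concern holds. The stated ground does not justify leaving the microbiome analyst unblinded, and the protocol does not say when the arm becomes known. The exposure is 1 of 6 named secondary measures, at two post-baseline times. Primary serum TMAO is not directly affected, because its analysts are blinded. Sample size, power and type I error are untouched. The documents do not allow the size or direction of any bias to be estimated.

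The conclusion assumes that no unstated technical step requires the true arm. The specimen counts assume that all 30 participants give stool at all three visits. This is a change that should be made, not a fault that undermines the trial; confidence is medium.

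**What to change.** Replace the exception in II.C.2 with text such as:

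> The microbiome analyst is blinded to treatment arm and works from study ID and visit only until specimen processing, exclusions and the diversity and composition measures are fixed in writing; the investigational pharmacy then releases group codes as A/B, and the arms are identified once the comparison is final.

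If a step truly needs the true arm, name it, say when the arm is released for it, and limit unblinding to that step.

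The cost is small. The processing, exclusion and measure rules must be written down before codes are released, and the pharmacy, which already holds the assignment, must release information in two stages. No added patients, visits or specimens are needed. The benefit is surest for the 30 baseline specimens and for decisions fixed before release. For the 60 later specimens masking may be only partial.
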